# 4.3.2 Total Number of Study Sites/Total Number of Subjects Projected

Enrollment for the study will continue until 54 participants have been enrolled.

HHRI will serve as the only site for this study.

### 4.3.3 Use of Vulnerable Populations and Patients Who Opt Out of Research

This study focuses on adults experiencing type 2 diabetes who have experienced recent homelessness per the HEARTH Act definition (Box). This is justified given the premature morbidity and mortality of this population from diabetes and related comorbidities. While not formally considered a vulnerable population, DH are a population requiring special attention with regard to safety and respectful engagement in research.

A consent quiz will be used to ensure that no individuals unable to consent are recruited similar to protocols used in part 2 of this study (HSR#20-4863). See *Consent Quiz*.

Furthermore, we will continue working closely with community providers in this area and our multi-stakeholder team to ensure we achieve cultural congruence with the ways we approach and engage this population in research as well as with the planned study protocols.

No patients who have chosen to opt out of research in their annual consent process through the health system will contacted about the study although they will be allowed to participate if they reach out to study staff in response to flyers or other community invitations.

### 4.5 Inclusion and Exclusion Criteria

#### 4.5.1 Inclusion Criteria

Inclusion criteria:

- 1. Age 18 yrs. or older
- 2. English-speaking
- 3. Recent homelessness by federal definition (HEARTH ACT)
  - a. Any housing instability in the last 12 mo. (includes supported housing or worry about paying rent)

- b. Significant housing instability in the last 24 mos. (includes any stay in shelter, outside, or places not meant for human habitation)
- 4. Self-reported diagnosis of type 2 diabetes, later verified in medical record
- 5. Verification of hemoglobin A1c value at or above 7.5% by study-administered test at baseline 1 visit
- 6. Plan to stay in local area or be reachable by phone for the next 24 weeks
- 7. Willingness to work on medication adherence and diabetes self-care

### 4.5.2 Exclusion Criteria

- 1. Inability to provide informed consent (e.g., presence of a legal guardian, prisoners)
- 2. Active psychosis or intoxication precluding ability to give informed consent
- 3. Pregnant or lactating people.

Subjects that do not meet all of the enrollment criteria may not be enrolled. Any violations of these criteria must be reported in accordance with IRB Policies and Procedures.

#### 5 STUDY PROCEDURES

### 5.1 Qualifying Visit

## 5.1.1 Eligibility, Screening Visit

As outlined in Table 1, before consent, interested participants will complete a screening. This will cover inclusion and exclusion criteria and briefly describe the intervention to ensure the participant is aware and willing to commit to study.

### 5.1.2 Baseline Assessment and Run-in

After the screening visit, after the participant's signed consent at baseline assessment visit #1, the medical record will be accessed. Participants' diabetes diagnosis, A1c results, medication list, frequency of refills, primary care team, and pattern of clinic/emergency department/hospital visits will be abstracted and recorded for the previous 12 months. If patients are found not to have diabetes at this point, they will be excluded from the study. We will also process their point-of-care A1c after visit #1 to ensure eligibility.

If patients are confirmed to be eligible based on medical record review, we will proceed with baseline visit 2 which can be done remotely or in-person.

As outlined in Table 1 above, the screening visit and baseline assessment visits will collect:

- Review Inclusion/Exclusion Criteria
- Informed Consent, HIPPA authorization
- Demographics/Medical History/Medication list
- Release of information for health systems used in last 12 mo.
- Release of information for insurance claims data in the last 12 mo.
- Biometrics: BP, height and weight, hemoglobin A1c (A1c)
  - O Alc testing involves the collection of a 1.5 μL blood sample via fingerstick or venipuncture
- Patient-reported outcome survey items (See Table 1)

### 5.2 Study Intervention

For participants randomized to the intervention group, they will be offered 10 coaching sessions over 12 weeks. These will be conducted in-person, via secure video, and/or by phone-based per participant preference and COVID-19 safety protocols. The treatment will center on providing diabetes education, motivational and goal-setting support, and resource and care coordination (Figure 2).

In-person assessment visits will be conducted at private spaces convenient to the participant including Hennepin Healthcare, Health Care for the Homeless sites, or at participant homes (see *Home Visit Protocol*).

All in-person assessment and treatment visits will follow current guidance from HHRI and Hennepin Healthcare about social distancing and use of personal protective equipment.

In-person treatment visits will be arranged that may include the participants home

Video visits will be conducted via a secure Zoom or Teams link (using HHRI, Hennepin Healthcare, and/or Hennepin County HIPAA secure technology) or Facetime if the participant is using an Apple device.

Phone visits will be conducted via a study or office phone or the PI's work phone. If participants have no working phone, a study phone will be issued to participants and will sign a Study Issued Cell Phone/Tablet Agreement (See *Phone/Tablet Agreement*).

Psychological approaches of behavioral activation and motivational interviewing will be used along with provision of educational materials and tools to support behavior change (See *Tools and Education Materials*). Coaches will tailor which tools and educational materials are given to which participants depending on participant need as well as the specific goals that are mutually set. E.g.) A participant with 10 medications per day may benefit from a pillbox with AM and PM slots. E.g.) A participant with many appointments for behavioral and physical health care may benefit from a pocket calendar. Financial value of tools ranges from \$4.99 (glucose log book) to \$17.91 (Adhesives for Continuous Glucose Monitor).

Approved communication channels will be used to support participant's goal setting (e.g. reminders) and arrange study related visits.

Participants will be offered up to 10 treatment visits over 12 weeks and monthly booster calls from weeks 12-24.

#### 5.2.1 Visit 1

The first visit will immediately follow the baseline #2 visit and be conducted in person whenever possible. The goals of the first visit are to (a) establish rapport, (b) assess baseline diabetes medication adherence and self-care behaviors, (c) describe the rationale for the treatment. The interventionist will get to know the participant and discuss things of importance in their life. She will complete a detailed assessment of prescribed diabetes medications and use of pharmacies and health care clinics/hospitals supplementing with data from the medical record as needed. The interventionist will also:

- Review boundaries for sessions, confidentiality, and mandated reporting
- Educate the patient on the rationale of behavioral activation and motivational interviewing
- Assess co-morbidities (e.g. mental illness, substance use disorder, heart disease) and contextual factors (e.g. housing status, social supports, food security)
- Assess existing diabetes care team; refer if no team in place.
- Assign self-monitoring goals per behavioral activation

### 5.2.2 Visit 2

The goals of the second visit are to complete a values assessment and provide relevant/needed health behavior tools. The interventionist will use a list to prompt the values assessment based on the Valued Living Questionnaire.  She will:

- Identify participant values
- Provide health behavior tools as desired/needed (e.g., pill boxes, calendar; see *Tools and Education Materials* for details)
- Identify valued activities goals to promote diabetes medication adherence and psychosocial wellness specific to the participant's values and context
- Problem-solve foreseeable barriers to behavior change goals

#### 5.2.3 Visits 3-5

The goals of visits 3-5 will be to advance the practice of behavioral activation and motivational interviewing to promote improved diabetes knowledge/confidence, and reduced logistical and emotional barriers specifically related to medication and other diabetes adherence. During these visits the interventionist will:

- Review engagement in health and wellness-promoting valued activities
- Identify valued activities goals to promote diabetes medication adherence and psychosocial wellness specific to the participant's values and context
- Problem solve foreseeable barriers to emergent behavior change
- Assess for inclusion of diet, exercise goals to enhance diabetes adherence goals

#### 5.2.4 Visits 6-8

The goals of visits 6-8 are to continue to support behavior change related to diabetes medication adherence. During these visits the interventionist will:

- Introduce advanced or challenging valued activity goals
- Explore ways to increase synergy between psychosocial wellness and diabetes health behavior goals

### 5.2.5 Visits 9-10

The goals of visits 9-10 are to emphasize maintenance of behavior change achieved during earlier weeks and plan for sustainability. During these visits the interventionist will:

Plan and implement strategies to maintain long-term diabetes adherence goals

### 5.2.6 Intervention group booster calls

Interventionists will offer monthly booster calls after the end of the intervention period (approx. 12-14 weeks post-enrollment), and prior to the follow-up assessment visit #2. Contact will be limited to a once-monthly to reinforce planned behavioral activation goals, update participant contact information, and arrange final follow up visit.

### 5.2.7 Comparison Group

Participants randomized into the comparison group will receive one 15 to 30-minute diabetes education session. Interventionists (coaches) will read the content of 3 diabetes educational handouts about (1) general descriptions of type 2 diabetes, (2) healthy eating, and (3) physical activity. Handouts are produced in alignment with American Diabetes Association guidelines by a community group (https://learningaboutdiabetes.org/) and have been used in previous diabetes behavioral trials with participants in low-income situations. Participants will receive a standard pillbox at this visit. Participants will receive a resource sheet with referral information to establish health care, mental health support, or to access local resources for housing, food, and other basic needs.

Comparison group participants will be contacted by the study staff (non-interventionists) once-monthly starting 4 weeks after their education session through the final assessment visit. Booster calls will update participant contact information and remind them of the timeline for follow-up assessments.

### **5.2.8** Follow-up Assessments

The follow-up assessments will be completed by a blinded research staff member. The staff person will assess:

- Vital Signs: BP
- Height and Weight
- Hemoglobin A1c
- Medication review
- Patient-reported measures, see Table 1 for timeline and specific measures

#### 5.3 Unscheduled Visits

Contact between the study team and participant during the 24-week study period will be encouraged. This will include reminders of study-related assessments and coaching visits.

The interventionist will work with intervention participants to set treatment goals related to improved diabetes care. These may include between-visit text messages, calls, e-mails, or private messages on secure social media platforms per the participant's preference. These will be done with input and agreement by the participant. The interventionist will also respond to participant-initiated between visit communications.

Study staff will respond to participant-initiated communications from comparison group participants. They will refer participants to locally available resources on the handout for any expressed needs.

Should communications become too frequent or surpass agreed upon boundaries with any participants, staff will be guided to set boundaries and limit contact by Drs. [name] and/or [name].

### 5.4 Concomitant Treatment

All prior and concomitant diabetes care in the year prior to the screening visit and through the end of the study will be recorded via self-report.

**5.5 Rescue Medication Administration** *Not applicable in this behavioral trial.* 

### 5.6 Subject Completion/Withdrawal

Subjects may withdraw from the study at any time without prejudice to their care. They may also be discontinued from the study at the discretion of the Investigator for lack of adherence to study treatment or visit schedules and adverse events (AEs). If the Investigator becomes aware of any serious, related adverse events after the subject completes or withdraws from the study, they will be recorded in the source documents and on the case report form.

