### 4.2 Allocation to Groups and Blinding

Participants will be randomized to either the intervention or a control group (1:1). Randomization will be stratified by housing type (unstable (e.g., shelter, staying outside) vs.

more stable (e.g., worry about rent payment, supportive or transitional housing)). Randomization will occur after baseline assessment visit #2 via REDCap. Staff who conduct who conduct the follow-up assessment visits will be blind to condition.

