### 5.6.1 Early Termination Study Visit

Any participant who withdraws will be contacted by the PI to be offered the opportunity to complete any outstanding assessment visits with compensation.

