# **6.3** Pharmacokinetic Evaluation Not applicable

# 6.4 Safety Evaluation

Subject safety will be monitored by adverse events and rates of early termination of the study. We will also follow safety protocols in case we identify dangerous blood pressure, or heart rate values at baseline or follow-up assessment visits. See Section 8 for details.

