#### 7 STATISTICAL CONSIDERATIONS

# 7.1 Primary Endpoint

The primary endpoint of this study is the satisfaction of participants in this pilot randomized trial (via CSQ-8).

The feasibility and acceptability of study protocols for recruitment, retention, and randomization are also important. We will assess this by measuring our ability to recruit and retain participants, and the assessment and treatment visits we can deliver (i.e., participant's attendance and follow-up with scheduled sessions and treatment activities). In addition to above outcomes, we will carefully track the number and types of between-treatment communications with participants (who initiated communication; form of communication: text, calls, e-mails, etc.).

We will consider the study feasible if we enroll 75% of those screened who meet inclusion criteria, and 75% of enrolled participants complete at least one follow-up. We will consider 50% session attendance as indicative of feasibility. We will consider the intervention acceptable if 70% of participants are satisfied and would recommend it to others.

We will also analyze our primary clinical endpoint of change in A1c between intervention and comparison groups between baseline follow-up visit #1 (approx. 12-16 weeks)

if it changes from baseline to between intervention.

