# 7.4.1 Efficacy Analysis

We will use summary statistics (mean, standard deviation) to examine CSQ-8 scores for all participants. We will use t-tests to examine the differences in CSQ-8 scores between the intervention and comparison groups; we hypothesize no difference. We will also examine the experiences of White vs. Black, Native American, and Hispanic participants. We will also generate summaries of the age, gender, and race/ethnicity of people at the highest and lowest quintiles of CSQ-8 scores.

We will use generalized linear models to compare changes in A1c and medication adherence (ARMS-D and ASK-12) over time in intervention vs. comparison groups. We will control for baseline differences and changes in housing status over time. Adherence will also be examined with pharmacy refill data which we will compare to self-report (ARMS-D and ASK-12). We will use an intention-to-treat approach including all randomized participants; multiple imputation will generate data for those lost to follow-up. Similar modeling approaches will compare psychological wellness, blood pressure, and health care use outcomes.

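### Section 5.6 lets non-attendance end participation in the whole study, not just coaching, so outcome data can be lost according to engagement and unequally by arm

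*Combined protocol and SAP*

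**What the plan says.** Section 5.6 first lets participants withdraw freely, then adds the investigator's power: "They may also be discontinued from the study at the discretion of the Investigator for lack of adherence to study treatment or visit schedules". No number of missed sessions or visits is given, and discontinuation is from the study as a whole.

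Four other places bear on what happens next.

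- Section 4.1.3 makes eligibility for follow-up depend on having finished the planned sessions or having asked to stop early.
- Section 5.6.1 provides a route back to assessment: "Any participant who withdraws will be contacted by the PI to be offered the opportunity to complete any outstanding assessment visits". It does not name participants whom the investigator discontinues.
- Section 7.4.1 sets the analysis: "We will use an intention-to-treat approach including all randomized participants", with multiple imputation for those lost to follow-up.
- Section 6.4 states: "Subject safety will be monitored by adverse events and rates of early termination of the study".

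Section 7.1 makes the same behaviour an outcome. The study is feasible if, among other things, "75% of enrolled participants complete at least one follow-up", and session attendance is a further criterion. CSQ-8 satisfaction is the primary endpoint. Table 1 schedules it at follow-up visit 1 only.

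**The concern.** A feasibility pilot has to measure non-attendance. Under section 5.6 non-attendance can instead become the reason for no longer measuring the participant.

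Exposure to the rule differs by arm. Coaching participants can fall short on treatment for 12 weeks, whereas the comparison arm's treatment is normally complete on the day of randomisation. The people most exposed can be foreseen: section 2 reports that in part 2 engagement was weaker among the least stably housed, and housing stability is the stratification factor.

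At stake are the retention result, the completeness of A1c and CSQ-8 in the arm under test, and the meaning of early termination as a safety measure. All of these inform the later, fully powered trial.

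**Working it through.** **Inputs from the documents.** "Enrollment for the study will continue until 54 participants have been enrolled" (section 4.3.2), allocated 1:1 (section 4.2), so 54/2 = 27 per arm if all enrolled are randomised. In the coaching arm "they will be offered 10 coaching sessions over 12 weeks" (section 5.2). The comparison arm has one session, on the day of baseline visit 2 (section 5.2.7, Table 2). Both arms have two follow-up visits (section 4.3.1). Section 7.5 gives no dropout rate, SD, effect size or power, so there is no plan figure to reproduce. Every other rate below is an assumption.

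**Step 1: exposure by arm.** Session 1 falls on the day of baseline visit 2 in both arms.

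- Treatment sessions that can be missed afterwards: coaching 10 − 1 = 9; comparison 1 − 1 = 0.
- Follow-up visits that can be missed: 2 in each arm.

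The treatment part of the rule is therefore almost wholly a coaching-arm rule; the visit part is shared.

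**Step 2: the passive non-attender.** Take a coaching participant who stops attending and says nothing. Under 4.1.3 this person has neither finished the sessions nor asked to stop, so is not eligible for follow-up. Under 5.6 the investigator may end study participation. Under 5.6.1 an offer of assessment is made if this counts as withdrawing, which the text does not settle. Under 7.4.1 the person stays in the analysis, with imputed outcomes. A comparison participant who had the single session already meets the 4.1.3 condition, so that condition also bears mainly on coaching.

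**Step 3: retention.** Cut-off: 0.75 × 54 = 40.5, so 41 are needed and at most 54 − 41 = 13 may lack a follow-up.

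- Simple case: 43/54 = 79.6% passes. If four of those 43 are removed without assessment, 39/54 = 72.2% fails.
- Less favourable to the concern: suppose k low-engaging coaching participants would have had only 50% retention if kept, and everyone else has retention p. Expected retention is [(54 − k)p + 0.5k]/54 if they are kept, and (54 − k)p/54 if they are removed unassessed.
  - p = 0.80, k = 4: 42/54 = 77.8% against 40/54 = 74.1%.
  - p = 0.80, k = 8: 40.8/54 = 75.6% against 36.8/54 = 68.1%.
- Exact binomial chance of reaching 41:

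| p | k | kept | removed |
|---|---|---|---|
| 0.80 | 4 | 0.699 | 0.444 |
| 0.80 | 8 | 0.549 | 0.080 |
| 0.85 | 4 | 0.925 | 0.791 |
| 0.85 | 8 | 0.825 | 0.293 |

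**Step 4: attendance.** The denominator is not defined. Assume 6 of 10 sessions for those kept, 1 of 10 for those removed, and k = 8. Over all 27 × 10 = 270 sessions, attendance is (19 × 6 + 8 × 1)/270 = 122/270 = 45.2%. If the removed leave the denominator, it is 60.0%. These fall on opposite sides of the 50% criterion in section 7.1. With k = 4 the first figure is (23 × 6 + 4)/270 = 52.6%, and nothing flips. The synopsis gives 70% as the attendance criterion; against that, all three figures fail.

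**Step 5: A1c and CSQ-8.** If k of 27 coaching participants have a change d points worse and are left out, or imputed as though engaged, the coaching mean shifts by (k/27) × d. For k = 4 and d = 1.0 this is 4/27 = 0.15 points in favour of D-HOMES. It is a limiting case, because the imputation model is not described. For CSQ-8, anyone removed before follow-up visit 1 and not assessed has no score. The imputation sentence in 7.4.1 sits with the A1c and adherence models, and whether it covers CSQ-8 is not stated.

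**The case against.** The strongest reply is that this is a gap in wording within a plan that otherwise works hard to retain people: monthly contact in both arms, a follow-up window extending to 30 weeks, and special attention to those who end early. The power is permissive, and nothing suggests it would be used often. That stands, and it is why the conclusion says the rule can change results, not that it does.

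Several stronger readings are tempting and are not supported.

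- **Only coaching participants can trigger the rule.** The clause also covers visit schedules, and both arms have two follow-up visits. The imbalance is large but not exclusive.
- **The rule contradicts intention-to-treat.** Section 7.4.1 keeps all randomised participants and imputes. Discontinuation creates missing outcomes; it does not shrink the analysis set. What remains is the risk that missingness depends on engagement in ways the undescribed model does not capture.
- **Retention could be moved in either direction.** Dropping the four from the denominator gives 39/50 = 78%, but the criterion refers to enrolled participants, and a discontinued participant was still enrolled. Removal can only lower this figure.
- **Discontinued participants are shut out of assessment.** The last sentence of section 5.6 divides participants into those who complete and those who withdraw, and 5.6.1 is headed as an early-termination visit, so it can be read to include them. The text is ambiguous, not exclusionary.
- **Administrative removals will be read as harm.** Adverse events are monitored as well, with quarterly review of both groups. The fair point is only that the termination rate would mix causes.

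Claims data are to be obtained for all participants at study end, so refill-based adherence need not be lost.

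**Conclusion.** The concern holds in a limited form. Section 5.6 does not separate the end of coaching from the end of follow-up. Section 4.1.3 reinforces the gap for passive non-attenders, and section 5.6.1 does not clearly close it. If the power is used, retention can only fall, and A1c and CSQ-8 can go missing more often among poorly engaged coaching participants. Imputation reduces that risk but does not remove it. The early-termination rate would also mix administrative with other causes, unequally by arm.

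The size is illustrative. Retention has a margin of 13 missing participants in 54, and four removals can cross it (80% to 72%) if those four would otherwise have completed. With 50% retention among them and 80% elsewhere, the chance of passing falls from 0.70 to 0.44. The attendance and A1c figures depend on assumed inputs and show direction only. The documents do not show that the A1c comparison will be biased in favour of D-HOMES.

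**What to change.** Reconcile sections 4.1.3, 5.6, 5.6.1 and 7.4.1 so that they give one answer for a participant who stops attending:

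1. State that non-attendance is recorded as an outcome and does not by itself end follow-up assessment or the collection of records and claims, unless consent is withdrawn.
2. Word section 5.6.1 to cover participants who withdraw or are discontinued.
3. Remove the section 4.1.3 condition as a bar to follow-up.
4. Keep all randomised participants in the retention denominator, and all randomised coaching participants, at 10 sessions each, in the attendance denominator. Settle the 50% and 70% attendance criteria at the same time.
5. For section 6.4, report ended coaching separately from study withdrawal, by arm and reason.

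The grounds for ending coaching remain with the investigators; this change concerns only whether outcomes are still collected.

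The cost is a wording amendment, some already scheduled visits attempted in people who have stopped coaching, and possibly a less favourable attendance figure. Assessments missed in the meantime cannot be recovered once the follow-up windows close.
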